objective outcomes: cancer recurrence and complications; and subjective outcomes: health related quality of life, psychological well-being, satisfaction with decision and satisfaction with care. **Outcomes Assessment:** As part of Specific Aim 2, following instruments will be used to measure preferences for participation in treatment decision, decision conflict and physician trust for both intervention group and the usual care control group at baseline, immediately after treatment decision, but prior to initiation of treatment. **Control Preferences Scale (CPS):** The CPS assesses the role that patients want to play and perceive playing in treatment decisions [259]. It consists of five sort-cards to assess different roles in decision making, ranging from a fully active to a fully passive role. This survey will be administered at baseline only. **Decision Conflict Scale (DCS):** The DCS is based on a conceptual framework of decision conflict, which is a state of uncertainty about which course of action to take. This scale is well studied in cancer area and has good psychometric properties [260]. We will administer this survey at baseline (before treatment). **Patient Trust-Wake Forest Physician Trust Scale:** This 10-item instrument is

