based on a multi-dimensional conceptual model of trust and measures trust in physicians and other health care providers [128-130]. Compared with previous scales, it showed improved internal consistency and variability [129, 131-132, 261]. Trust is measured by the sum of the 10 item scores, ranging from 10 to 50, with a higher score indicating higher trust [129, 131-132, 261]. As part of Specific Aim 3, the following outcomes will be measured for both intervention group and the usual care control group after initiation of treatment. Treatment choice: We will obtain data on primary and secondary treatments received, such as active surveillance, RP, RALP, EBRT, BT or PT via self report and verified from medical chart review. Satisfaction with Decision (SWD): The SWD scale measures satisfaction with healthcare decisions. It was developed in the context of postmenopausal hormone-replacement therapy decisions. The six-item scale has excellent reliability (Cronbachs alpha = 0.88) [262]. Regret scale: Regret represents the unsettling feeling of having made a poor choice of treatment, persistent doubt, and a wish to change one's mind. The Regret scale is defined by three items that assess (1) the mans wish that he could change his mind about the kind of treatment he has received, (2) his feeling that he would be better if he had chosen the other treatment, and (3) whether he is bothered by the fact that other men received very different treatments for their PCa [33]. This scale exhibited good psychometric properties and has been extensively studied [33, 174, 263-265]. Following objective and subjective outcome measures will be assessed at baseline and at each post-treatment follow-up period (3,6,12 and 24 months) for intervention group and usual care control group. Biochemical recurrence: We will define progression of PCa as a change in PCa stage to an advanced stage or PSADT, post treatment [11, 44-45, 55, 160, 203]. We will obtain PSA data at baseline, prior to treatment, and post treatment at three months interval for 18 months. A PSA value of greater than 0.2 ng/ml indicates disease recurrence for surgery patients. For radiation therapy patients, we will adopt the Houston / Phoenix definition of the current PSA nadir + 2 ng/mL, with date of failure determined at call as the biochemical recurrence after radiation therapy [11, 44-45, 55, 160, 203]. Any treatment within six-month of diagnosis will be considered as adjuvant (review by investigators Drs. [name], [name], and [name]). D.2.4.3.2 Medical complications: We will identify complications that occur during either index or subsequent hospital admissions within 30 days of treatment [266]. Alibhai, et al. (2005), has grouped complications after RP into seven mutually exclusive categories: cardiac; respiratory; genitourinary; wound or bleeding; vascular; miscellaneous medical; and miscellaneous surgical [266]. Similarly, a list of complications for each treatment type will be developed by literature review and the physician investigators and consultants. Generic HRQoL- Medical Outcome Study Short Form: HRQoL data will be obtained using the Medical Outcome Study Short Form (SF-36) a multi-item scale that assesses eight health domains. This instrument can be self-administered or administered by a trained interviewer, either in person or by telephone. It has been tested extensively for reliability ($r=0.80 - 0.93$) and validity (Cronbachs $=0.92$). Scores on each sub-scale range from 0 to 100, with higher scores indicating better HRQoL [267-271]. Prostate Cancer HRQoL- Expanded Prostate Cancer Index (EPIC): The EPIC was developed for comprehensive assessment of HRQoL in men with PCa. It is a 50-item expanded edition of the 20-item UCLA Prostate Cancer Index (PCI) and complements other instruments by measuring a broad spectrum of urinary, bowel, sexual and hormonal symptoms. It has good psychometric properties: test-retest reliability and internal consistency are high for EPIC and for most of the subscales [189, 272-273]; construct validity was established using SF-36 as a generic core measure and a cancer-related HRQoL instrument, the Cancer Rehabilitation System-Short Form [189, 272-273]; and is easy to understand and complete [192]. American Urological Association Symptom Index (AUA-SI): The AUA-SI, a clinically sensible, reliable, valid and responsive index widely used for clinical and research purposes [274], has good internal consistency (Cronbachs $=0.86$), excellent test-retest reliability ($r=0.92$) and sensitivity to change with preoperative scores decreasing from a mean of 17.6 to 7.1 by four weeks after prostatectomy ($p<0.001$). D.2.4.3.6 Patient Satisfaction Questionnaire (PSQ-18): This 18-item survey [a shorter version of the original Patients Satisfaction Questionnaire [275], assesses global satisfaction with medical care and satisfaction with six aspects of care: technical quality; interpersonal manner; communication; financial aspects of care; time spent with doctor; and accessibility of care. It has demonstrated good internal consistency (Cronbachs $=0.86$) and excellent test-retest reliability ($r=0.92$). Memorial Anxiety Scale for Prostate Cancer (MAX-PC): The 18-item MAX-PC identifies three aspects of PCa-related anxiety. It has high internal consistency and concurrent and discriminant validity[276]. The Center for Epidemiologic Studies Depression (CES-D) scale: This 20-item, self-report scale to identify depression in the general population covers major components of depression, with an emphasis on affective components: depressed mood; feelings of guilt and worthlessness; feelings of helplessness and hopelessness; psychomotor retardation; loss of appetite; and sleep disorder [277]. Potential confounding variables: Disease severity: We will adjust for disease severity using information on PCa stage or TNM stage, grade and histology from electronic medical records. Gleason score: The Gleason score is a sum of the predominant pattern and the second most

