
among treatment features will be calculated in patient-specific utilities or part-worths associated with the attribute levels in the study. For other outcomes, participants will receive the following surveys via mail within 1-2 weeks after enrollment and prior to treatment initiation: SF-36, EPIC, AUA-SI, regret scale, CES-D, MAX-PC, SWD, PSQ-18, CPS, DCS and trust scale. Demographics, health and family history, clinical covariates and cancer progression data will be collected at 3, 6, 12 and 24 month follow-up. Histological tumor grade Gleason score and PSA and annual Elixhauser comorbidity score [257-258] will be obtained from the Pennsylvania Integrated Clinical and Research Database (PICARD), a UPHS, Fox-Chase Cancer Center electronic database, and PVAMC administrative and patient HER database. Retention and survey administration: During enrollment, importance of active participation will be emphasized. All participants will complete self-administered surveys at baseline within 1-2 weeks after enrollment (prior to treatment initiation) and again 3,6,12 and 24 months post-enrollment (see Appendix for copies of instruments, consent and medical chart review form). Non-respondents will be contacted via telephone after 10 days. In case of non-response due to death, cause of death will be noted and the physician investigators will determine cause of death (PCa or non-PCa related). The PCa conjoint analysis task, DCS, CPS and trust scale will be administered at baseline only, immediately after diagnosis of PCa and before treatment decision. D.2.4 Outcomes Assessment: D.2.4.1 As part of Specific Aim 2, following instruments will be used to measure preferences for participation in treatment decision, decision conflict and physician trust for both intervention group and the usual care control group at baseline, immediately after treatment decision, but prior to initiation of treatment. D.2.4.1.1 Control Preferences Scale (CPS): The CPS assesses the role that patients want to play and perceive playing in treatment decisions [259]. It consists of five sort-cards to assess different roles in decision making, ranging from a fully active to a fully passive role. This survey will be administered at baseline only. D.2.4.1.2 Decision Conflict Scale (DCS): The DCS is based on a conceptual framework of decision conflict, which is a state of uncertainty about which course of action to take. This scale is well studied in cancer area and has good psychometric properties [260]. We will administer this survey at baseline (before treatment). D.2.4.1.3 Patient Trust-Wake Forest Physician Trust Scale: This 10-item instrument is based on a multi-dimensional conceptual model of trust and measures trust in physicians and other health care providers [128-130]. Compared with previous scales, it showed improved internal consistency and variability [129, 131-132, 261]. Trust is measured by the sum of the 10 item scores, ranging from 10 to 50, with a higher score indicating higher trust [129, 131-132, 261]. D.2.4.2 As part of Specific Aim 3, the following outcomes will be measured for both intervention group and the usual care control group after initiation of treatment. D.2.4.2.1 Treatment choice: We will obtain data on primary and secondary treatments received, such as active surveillance, RP, RALP, EBRT, BT or PT via self report and verified from medical chart review. . D.2.4.2.2 Satisfaction with Decision (SWD): The SWD scale measures satisfaction with healthcare decisions. It was developed in the context of postmenopausal hormone-replacement therapy decisions. The six-item scale has excellent reliability (Cronbachs alpha = 0.88) [262]. D.2.4.2.3 Regret scale: Regret represents the unsettling feeling of having made a poor choice of treatment, persistent doubt, and a wish to change one's mind. The Regret scale is defined by three items that assess (1) the mans wish that he could change his mind about the kind of treatment he has received, (2) his feeling that he would be better if he had chosen the other treatment, and (3) whether he is bothered by the fact that other men received very different treatments for their PCa [33]. This scale exhibited good psychometric properties and has been extensively studied [33, 174, 263-265]. D.2.4.3 Following objective and subjective outcome measures will be assessed at baseline and at each post-treatment follow-up period (3,6,12 and 24 months) for intervention group and usual care control group. D.2.4.3.1 Biochemical recurrence: We will define progression of PCa as a change in PCa stage to an advanced stage or PSADT, post treatment [11, 44-45, 55, 160, 203]. We will obtain PSA data at baseline, prior to treatment, and post treatment at three months interval for 18 months. A PSA value of greater than 0.2 ng/ml indicates disease recurrence for surgery patients. For radiation therapy patients, we will adopt the Houston /Phoenix definition of the current PSA nadir + 2 ng/mL, with date of failure determined at call as the biochemical recurrence after radiation therapy [11, 44-45, 55, 160, 203]. Any treatment within six-month of diagnosis will be considered as adjuvant (review by investigators Drs. [name], [name], and [name]). D.2.4.3.2 Medical complications: We will identify complications that occur during either index or subsequent PRINCIPAL INVESTIGATOR (LAST, FIRST, MIDDLE): [name] PCORI Research Plan: Research Strategy 11 hospital admissions within 30 days of treatment [266]. Alibhai, et al. (2005), has grouped complications after RP into seven mutually exclusive categories: cardiac; respiratory; genitourinary; wound or bleeding; vascular; miscellaneous medical; and miscellaneous surgical [266]. Similarly, a list of complications for each treatment type will be developed by literature review and the physician investigators and consultants. D.2.4.3.3 Generic HRQoL- Medical Outcome Study Short Form: HRQoL data will be obtained using the Medical Outcome Study Short Form (SF-36) a multi-

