patients in decision (measured using CPS) using multi-nominal regression model to adjust for observed covariates. Then we will examine if these associations vary across intervention and usual care control groups. We then will repeat the model with other independent variables (decision conflict and trust). Next, we will test the association denoted by path c (direct effect of DCS, CPS, and trust on outcomes). For continuous outcomes (HRQoL, AUA-SI, MAX-PC, CES-D, SWD, and PSQ-18), we will compute area under the curve (AUC) for each measure for each patient. We will analyze AUC summaries with univariate linear models. In our main analysis we will analyze the series of functional status measures using linear mixed models that predict the outcome from time, independent variables and their interaction. We will repeat the analyses described for path c, this time by including treatment received in the models. We will test if the observed effects of DCS, CPS or trust on outcomes will be weaker after controlling for treatment. These analyses will be performed within and between groups (intervention and usual care controls). Specific Aim 3: Hypothesis: Prostate cancer patients in the intervention group undergoing conjoint analysis-value clarification exhibit improved treatment choice, satisfaction with decision, lower regrets, and improved objective and subjective outcomes. Analysis for Specific Aim 3 uses intent-to-treat approach: all randomized participants will be included regardless of whether they drop out of the intervention or study. Analysis will involve comparison of the primary outcomes between intervention and usual care control groups. Improved treatment choice is operationalized as the likelihood of low-risk PCa patients receiving active surveillance than active treatment, and will be compared between intervention and usual care control group. To allow for different trajectories of the outcome measures and to afford flexibility in making contrasts within participants over time and across participants, while simultaneously controlling for potential confounders, we propose the participant-specific or mixed effects linear model, in which the mean outcome depends on fixed covariates and random effects. The primary fixed effects will be indicators for intervention group and hospital. We will also stratify the analysis by type of treatment. The random effects represent the unobserved factors that lead to variation of the individual participants outcome. Random intercepts for each participant permit modeling of natural variation across participants at baseline. In addition, random slopes or random effects for the trajectory of each participant over time, allow for variation of each participant about a mean, overall trajectory across all participants. Although less robust to model misspecification, the mixed effects paradigm offers special flexibility in longitudinal data when exposures vary over time and when dropout and missed visits lead to unbalanced groups. The target of inference is the participant-specific response to treatment over time. At each time point of interest, we will estimate from the fitted model the difference from baseline in outcome for the treatment and control groups and test the difference between these differences. Both univariate and multivariate results will be reported in terms of Wald test, point estimates, and 95% confidence intervals. Specific Aim 4: Hypothesis 4: Prostate cancer patients whose treatment is more concordant with their values markers will experience improved subjective and objective outcomes. This specific aim s for intervention group only. We will analyze the association of the concordance between stated individual preferences and actual treatment received with objective (PCa recurrence and complications), subjective (HRQoL, psychological wellbeing, SWD, and satisfaction with care) outcomes, across treatment groups, adjusting for covariates. Association between the value markers (profiles) and measures of outcomes and personal and clinical characteristics: The value markers will be studied for their relationship with socio-demographic and clinical characteristics. We will also assess the association of value markers with outcomes. We will perform logistic regression with outcomes as the dependent variable and dummy variables for the utility-based profiles obtained earlier as independent variables. We will perform this evaluation with and without adjusting for patient attributes in the logistic model. For each case (adjusting and not adjusting for patient attributes), the evaluation of association between these profiles and outcomes will be based on a likelihood ratio test of the set of odds ratios corresponding to the dummy variables of the profiles. Additionally, we will perform a sequence of pair wise tests of comparisons of the profiles in terms of the proportion of type of treatment received based on the Holms multiple comparisons approach. This procedure is hierarchical in that it will identify the utility-based profile at the start of the process before making other comparisons, thus protecting the Type I error from additional comparisons. Specifically, Holms approach tests each pair-wise comparison in ascending order of p-values. Successively larger p-values have less rigorous alpha. The sequential Holm tests terminate after the first non-significant comparison so no subsequent comparison is significance. Concordance and its assessment: Understanding and respect for the patients preference and values is the main aspect of concordance [69, 73]. Thus a first step in concordance involves the physician extracting and understanding the patients view, followed by an agreement between the physician and patient regarding a management plan that integrates their views. There exist many definitions of concordance. For the purpose of this study, we operationalized concordance as agreement between a patients value markers and the attributes (or characteristics) of the treatment that

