
the patient receives (choice). Association of concordance between stated preference and attributes of treatment received will be studied separately for each treatment using Kappa statistics. The degree of concordance then will be used as an independent variable to test its association with outcomes. For objective/clinical outcomes (i.e., complications and PCa recurrence), we will test the hypothesis that degree of concordance is associated with PCa recurrence (measured by PSA doubling time). To evaluate the effects of concordance on biochemical recurrence of PCa, we will analyze PSA levels on the log scale over time using a mixed model approach. We also will apply survival analyses (Kaplan-Meier, logrank and Cox model) to model effects concordance of treatment and covariates on time to PSA recurrence. For subjective outcomes of urologic symptoms (AUA-SI), generic and prostate specific HRQoL, psychological well-being (CES-D, MAX-PC), satisfaction with decision and satisfaction with care, we will perform inferential analysis with t, chi-squared and non-parametric tests. Wilcoxon matched-pairs test will be used for comparisons within concordance and non-concordance groups. A concordance group will be defined as at least 75% agreement between values markers and treatment related attributes. We will perform sensitivity analysis to test robustness of results. Primary analyses will compare baseline with six and 24 months assessments, as literature suggests these are the clinically most relevant time points. Secondary analyses will compare baseline with three month and one year outcomes. Proportion returning to baseline over time will be compared using chi-squared tests, using procedures such as Bonferroni, Scheffé, and step-down Holm corrections to adjust for multiple testing. We will use loglinear regression models with psychological well being, HRQoL and satisfaction with care scores (log) as dependent variables, logistic regression with return to baseline as the dependent variable, and degree of concordance as the independent variable. For repeated measures outcomes we will use linear mixed models (Proc Mixed).

The following documents are currently attached to this item:

There are no documents attached for this item.

Deception

Does your project use deception?

No

Data confidentiality

- x Paper-based records will be kept in a secure location and only be accessible to personnel involved in the study.**

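### PSA recurrence has no rule for men on surveillance, yet Aim 3 compares it between arms in all randomised men while expecting more surveillance in the intervention arm

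*Combined protocol and SAP*

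**What the plan says.** The section on primary outcome variables lists "objective outcomes: cancer recurrence and complications" beside the subjective outcomes, and no secondary outcomes are named.

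- **Recurrence (D.2.4.3.1).** A general sentence reads "We will define progression of PCa as a change in PCa stage to an advanced stage or PSADT, post treatment", with no cut-off for doubling time. Two PSA rules follow: "A PSA value of greater than 0.2 ng/ml indicates disease recurrence for surgery patients", and "For radiation therapy patients, we will adopt the Houston /Phoenix definition of the current PSA nadir + 2 ng/mL". PSA is collected at baseline and "post treatment at three months interval for 18 months". No rule is given for active surveillance.
- **Complications (D.2.4.3.2).** These are "complications that occur during either index or subsequent hospital admissions within 30 days of treatment". A list for each type of treatment is still to be developed.
- **Aim 3 (Analysis Plan).** The hypothesis is better treatment choice and better objective and subjective outcomes in the intervention arm. "Improved treatment choice is operationalized as the likelihood of low-risk PCa patients receiving active surveillance than active treatment". The analysis set is intent-to-treat and covers every randomised man. Stratification by treatment type is also mentioned. The text does not say how surveillance men enter the recurrence or complication analysis.
- **Quota (Recruitment, and the power text under Accrual).** Enrolment continues until each of six treatment groups, surveillance included, holds 60 men per arm. Men beyond a full group have baseline data but no further follow-up.

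**The concern.** The intervention is meant to raise the share of low-risk men on surveillance, and those are the men for whom PSA recurrence has neither a threshold nor a starting date. A randomised comparison is only interpretable if the outcome can be determined for every man in the same way. Here, the proportion of men in whom it cannot be determined is itself something the intervention aims to change. A difference in recurrence between arms could then appear with no difference in cancer control. Because the handling of these men is unwritten, it could be chosen after the data are seen, and the choice can reverse the sign.

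Complications also lack a starting date for surveillance men. The issue there is milder and concerns interpretation.

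**Working it through.** **Figures in the plan.** The quota arithmetic reproduces: 60 × 2 × 6 = 720, and 720 / 0.9 = 800 men at baseline. Under the quota the surveillance share is 60 / 360 = 16.7% in each arm. The documents give no recurrence rate, low-risk share or expected shift in surveillance, and no power for recurrence by arm. All such inputs below are assumptions.

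**Inputs.** Surveillance share: a0 = 0.1667 in controls (from the quota) and a1 = 0.2667 in the intervention arm (assumed rise of 10 points). There are 360 men per arm. The event rate c in treated men, or the rate within each risk group, is the same in both arms, so the intervention has no effect on cancer control.

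**1. Surveillance men counted as event-free.** Arm rate = (1 − a) × c, so RR = (1 − a1) / (1 − a0) = 0.7333 / 0.8333 = **0.88**, whatever c is. With c = 10%, the rates are 8.3% v 7.3%. A rise of 20 points gives 0.6333 / 0.8333 = 0.76. For c from 5% to 30%, the chance of a significant result is 5% to 16% for the 10-point rise.

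If the men moved are low-risk, the shift is smaller. Let L be the low-risk share (40% to 50%), with recurrence of 5% in low-risk men and r in the others (15% to 25%), and surveillance only among low-risk men. Arm rate = (L − a) × 0.05 + (1 − L) × r.

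| L | r | Control | Intervention | RR |
|---|---|---|---|---|
| 0.40 | 15% | 10.17% | 9.67% | 0.95 |
| 0.40 | 25% | 16.17% | 15.67% | 0.97 |
| 0.50 | 15% | 9.17% | 8.67% | 0.95 |
| 0.50 | 25% | 14.17% | 13.67% | 0.96 |

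The absolute shift is 10 points × 5% = 0.5 percentage points throughout.

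**2. Surveillance men excluded.** With the same risk mix, each rate above is divided by (1 − a).

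| L | r | Control | Intervention | RR |
|---|---|---|---|---|
| 0.40 | 15% | 12.20% | 13.18% | 1.08 |
| 0.40 | 25% | 19.40% | 21.36% | 1.10 |
| 0.50 | 15% | 11.00% | 11.82% | 1.07 |
| 0.50 | 25% | 17.00% | 18.64% | 1.10 |

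The ratio is **1.07 to 1.10**, now against the intervention, because low-risk men have left the denominator.

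**3. Surveillance men held to the 0.2 ng/ml threshold, all assumed to exceed it.** Arm rate = (1 − a) × c + a. With c = 10%: 0.0833 + 0.1667 = 25.0% v 0.0733 + 0.2667 = 34.0%, so RR = **1.36**. With c = 5% it is 20.8% v 30.3% (1.46), and with c = 20% it is 33.3% v 41.3% (1.24).

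**4. Surveillance share held at 60 / 360 in both arms.** a1 = a0, and the ratio is **1.00** under all three rules.

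**The case against.** **The quota.** If exactly 60 surveillance men per arm are followed, the share is equal and the shift disappears. This stands for the followed cohort, and it defeats the inference a reader might draw that following the plan necessarily biases the arm comparison. It does not settle the matter, for four reasons:

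- The quota drops men after randomisation, while Aim 3 includes everyone randomised. Both cannot govern the same analysis.
- A fixed surveillance share leaves little room to show the improvement in treatment choice that Aim 3 predicts.
- At 26.7% surveillance, filling the other 300 places in an arm takes about 300 / 0.7333 = 409 men, even with the other five groups filling evenly and no attrition. The 800 expected at baseline give 400 per arm.
- One-sixth of each arm would still have no recurrence definition.

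**Direction.** A reader might infer that success on treatment choice automatically shows up as fewer recurrences. The documents do not support that. No text counts surveillance men as event-free, and the 0.2 ng/ml rule is confined to surgery. Nor is it right that surveillance men can never have an event: D.2.4.2.1 records secondary treatments, so a man who later has surgery or radiation can meet the PSA rules.

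**Complications.** Fewer complications because fewer men are treated is a genuine total effect under intent-to-treat. It should not be called bias.

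**Doubling time.** The analysis of recurrence by PSA doubling time belongs to Aim 4, which is confined to the intervention arm. It is not evidence of a conflicting endpoint in the arm comparison, and D.2.4.3.1 already names doubling time.

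**Stratification.** Stratifying by treatment type conditions on a choice made after randomisation, so it does not restore the randomised comparison.

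**Consequence.** The sample size rests on quality of life, which limits how much depends on recurrence. That is fair, but recurrence is still listed among the primary outcomes.

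**Conclusion.** The concern holds for PSA recurrence, conditionally. If the surveillance share differs between arms, as Aim 3 hypothesises, the recurrence comparison moves with no change in cancer control, and none of the three ways of handling surveillance men makes it a fair comparison. For a 10-point rise from 16.7%, the spurious ratio runs from 0.88 (0.95 to 0.97 if the men moved are low-risk), through 1.07 to 1.10, to 1.36. These values rest on the assumed shift, event rates and risk mix. Under the event-free rule the absolute shift is modest: 1 percentage point at a 10% event rate, and 0.5 points if the men moved are low-risk.

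Two stronger readings do not follow: that the plan as written must favour the intervention, and that both objective outcomes are biased. The quota could equalise the share, the direction is open, and the complication difference is a legitimate effect that needs careful reading. This should be settled before outcome data are seen.

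**What to change.** 1. For Aim 3, compare arms on one progression outcome that applies to all six treatment groups and is timed from randomisation. The stage-change component is the natural candidate. It is now tied to the period after treatment, so it must be extended explicitly to surveillance men, with a statement of what evidence of stage counts. D.2.3 already collects progression data at 3, 6, 12 and 24 months.
2. Report PSA recurrence only within the surgery group and within the radiation group, labelled as non-randomised. Do not enter surveillance men as event-free.
3. Keep the intent-to-treat comparison of complications as a total effect. Count them over a common follow-up period from randomisation that is long enough to include treatment, and present any difference beside the surveillance share in each arm.
4. Reconcile the quota text (Recruitment and Accrual) with the intent-to-treat set in Aim 3, so that it is clear which men are followed and analysed.

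The cost is mainly wording in the analysis plan, plus slightly wider chart abstraction, since chart review is already planned. The drawback is that stage-progression events are likely to be few within 24 months, so the arm comparison will be imprecise and should be described as such.
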